OFFICIAL TITLE: Oral Health Educational Methods in Adolescence

NCT number: **03216746**

Date:17/07/2018

Study Protocol and Statistical Analysis Plan

Study population and sample size

The investigation followed the parameters of the Declaration of Helsinki and was approved by the Human Ethics Committee of the Federal University of Paraná (case number 51712315.4.0000.0102). The description of this clinical trial followed the recommendations made by CONSORT and the extension to cluster randomized trials¹⁹. The study was registered in the clinicaltrials.gov database under number NCT03216746.

Clinical trial randomized by clustering involving four arms in a 1: 1: 1: 1 ratio to the four intervention groups. The randomized allocation was performed using the classes as sample units. The courses were ordered alphabetically by name and allocation was generated by the software *Stata* version 12.0. A total of 28 classes were selected and randomly allocated to an interventional group by a blinded investigator, which did not participate in the study. The analysis was done in the individual unit. Adolescents of both sexes, aged 14 to 19 years, enrolled in a technical high school in the city of Curitiba, Paraná, Brazil were evaluated. Written informed consent was obtained prior to randomization from the participant or from the legal guardian when the age of the participant was less than 18 years.

Exclusion criteria were: adolescents with some physical or mental condition that made interventions impossible and those using fixed orthodontic devices at the time of clinical examination. Cluster unit areas of technical education related to the

health area, including dental technician, were excluded. The duration of the study was from July to December 2016.

The comparison between two independent groups was used for the sample calculation considering the unequal variances. For this calculation, the outcome was considered the "knowledge score" (KS). In a pilot study, it was found that the standard deviation of the KS from the "oral guidance" group was 2.56, while in the "video" group it was 1.96. In the same study, the difference detected between the groups was 0.53 points in the knowledge score. Therefore, considering a 5% significance level and 80% statistical power, a sample value of 108 individuals was found for each group, totaling 216 participants. Estimating a loss of 35% for each group, the final sample totaled 317 individuals.

Pilot study

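### The stated 35% loss allowance does not give 317: keeping 216 analysable needs 333 (334 by group), and 317 at 35% loss leaves about 206

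*Combined protocol and SAP*

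**What the plan says.** The calculation is in the last paragraph under Study population and sample size. It compares two independent groups with unequal variances on the knowledge score, "considering a 5% significance level and 80% statistical power". The pilot standard deviations are 2.56 (oral guidance) and 1.96 (video), and "the difference detected between the groups was 0.53 points in the knowledge score". From these, "a sample value of 108 individuals was found for each group, totaling 216 participants". The next sentence makes the allowance for loss: "Estimating a loss of 35% for each group, the final sample totaled 317 individuals".

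Nothing else is shown between 216 and 317. The paragraph gives no inflation formula, design effect, finite-population correction or other adjustment.

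**The concern.** A loss allowance should turn the number needed for analysis into the number to enrol, so that the first is still met if the predicted loss occurs. Here 216, 35% and 317 appear in consecutive sentences, and no usual way of applying a 35% loss to 216 gives 317. The figure is also odd, whereas inflating two equal groups of 108 at the same rate would give an even total.

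Two things are at stake. A reader cannot reproduce the final sample size, although the document says that it follows CONSORT and its cluster extension. And if 317 was the number to enrol, the plan misses its own analysable target at its own loss rate.

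**Working it through.** **Inputs**, all from Study population and sample size: 108 per group; 216 in total; loss 35% in each group; final sample 317; standard deviations 2.56 and 1.96; difference 0.53; significance level 5%; power 80%. Sidedness is not stated, so two-sided is assumed unless noted.

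**Step 1. Try to reproduce 317.**
- Standard allowance, N/(1 − d): 216/0.65 = 332.3, so 333.
- The same by group: 108/0.65 = 166.2, so 167 per group and 2 × 167 = 334.
- The same with 216 split over four arms: 54/0.65 = 83.1, so 84 per arm and 4 × 84 = 336.
- The common mistake, N × (1 + d): 216 × 1.35 = 291.6, so 292.

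None of these gives 317. The standard allowance exceeds it by 16 (333) or 17 (334), and the common mistake falls 25 below it. Rounding cannot explain gaps of that size.

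**Step 2. What 317 does correspond to.**
- Loss at which 317 leaves 216: 1 − 216/317 = 0.319, about 32%. As a check, 216/0.68 = 317.6.
- Number left from 317 at 35% loss: 317 × 0.65 = 206.05, about 206, or 103 per group.
- Shortfall: 216 − 206 = 10, about 5% of the target.

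**Step 3. Effect on power if 108 per group gave 80%.** The standardised signal at 108 is 1.960 + 0.842 = 2.802. At 103 it is 2.802 × √(103/108) = 2.736. Power = Φ(2.736 − 1.960) = Φ(0.776) = 78.1%. The loss is about 2 percentage points.

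**Step 4. Effect on power with the stated inputs.** The two-group formula with unequal variances is

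n per group = (SD₁² + SD₂²)(z₀.₉₇₅ + z₀.₈₀)² / δ².

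- SD₁² + SD₂² = 6.5536 + 3.8416 = 10.3952.
- n = 10.3952 × 7.849 / 0.2809 = 290.5, so 291 per group (229 if one-sided), not 108.
- Power at 108: standard error √(10.3952/108) = 0.3102; 0.53/0.3102 = 1.708; Φ(1.708 − 1.960) = 40.1%.
- Power at 103: standard error √(10.3952/103) = 0.3177; 0.53/0.3177 = 1.668; Φ(1.668 − 1.960) = 38.5%.

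The loss error therefore costs about 1.5 percentage points on the stated inputs. All of these power figures are before any allowance for randomisation by class.

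**The case against.** The strongest reply is that 317 is not a calculated figure at all. The sentence is in the past tense, the document is dated July 2018, and the study ran from July to December 2016. An odd total looks more like a count of people than like two inflated groups. On this reading nothing was miscalculated; a realised number was joined to a planning sentence.

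This is possible, and the fix should allow for it, but it does not rescue the text. The sentence ties 317 directly to the 35% estimate. If 317 were enrolled, a 35% loss would still leave fewer than 216. If 317 is a realised count, the planned number to enrol is not given anywhere.

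The reply is right on two further points. First, a reader might infer that the trial itself under-recruited. The documents do not show this. They do not say that recruitment was capped at 317, and they describe 28 classes taught in groups of about 20, which would be some 560 students if each group was one class (an assumption). The 35% is also only an estimate; 317 would leave 216 if the loss were no more than about 31.9%.

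Second, a reader might charge the loss error with the low power of a comparison between two of the four arms. On the premise that 108 per group gives 80%, about 51 per arm (half of 103) gives about 49%. But the full 216, at 54 per arm, gives only about 51% on the same premise: Φ(2.802 × √0.5 − 1.960) = Φ(0.021). Almost all of that deficit comes from spreading a two-group calculation over four arms, and it does not measure this error.

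**Conclusion.** The sentence is wrong as written, whatever 317 represents. With the plan's own 216 and 35%, the number to enrol is 333 (334 by group). The printed 317 leaves about 206 at that loss and fits a loss of about 32%. This rests only on the plan's printed figures and on the usual meaning of a loss allowance.

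The consequence is small: ten analysable participants, and about 1.5 to 2 percentage points of power depending on the premise. It changes no analysis method, outcome or allocation.

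A reader might conclude that correcting the allowance restores 80% power, or that leaving it costs only a fall to 78%. The documents support neither. Both figures assume that 108 per group gives 80%, whereas the stated standard deviations and difference need about 291 per group and give about 40% at 108 (two-sided, Normal approximation, before clustering). That is a separate and larger fault in the base calculation, and correcting the loss allowance does not repair it.

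**What to change.** Correct the sentence in one of these ways:

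- State that 216 analysable participants with a 35% loss require 334 enrolled (167 per group).
- Keep 317 and state that it allows for a loss of only about 32%, or that it leaves about 206 analysable at 35%.
- If 317 is the number actually enrolled, say so and give the planned figure separately.

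Whichever is chosen, do not quote 78% or 80% power beside the corrected number while the 108 per group does not follow from the stated inputs. Recruitment ended in 2016, so this is a correction to the record. It costs one sentence, plus the admission that the printed total did not cover the stated loss.

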A pilot study was carried out with the objective of testing the suitability and methodological applicability of the instruments used. In addition, this step allowed us to verify the application dynamics of the instruments and the average time spent with each participant. Fifteen adolescents aged 14 to 19 years, with the same socioeconomic characteristics as the study population, were selected who did not participate in the main study. The methodological design was adequate; however, some terms of the questionnaire were modified to allow greater understanding on the part of the adolescents.

Interventions

Interventions were performed at the individual level within each cluster. The study included four phases (Figure 1), and the educational interventions or their different associations were evaluated through the knowledge score (KS) and oral

clinical indexes. In Phase I/baseline, the participants answered a questionnaire (pre-test) and were evaluated clinically. In phase II, the 28 classes were randomly allocated into two groups: 14 classes received oral guidance (OG) and 14 classes received video guidance (VG). Both methods (oral guidance and guidance by video) had the same thematic content. In the next phase (III), the groups were again divided into four groups (7 groups in each group), and for two of them, a smartphone App was developed so that reinforcement messages were sent during a period of 30 days. Shortly after this period (phase IV), the participants answered the questionnaire again (follow-up test) and were reassessed clinically.

Oral guidance with standardized content was performed by one of the researchers (GM) previously trained, and included aspects on general, oral health and, especially, on periodontal diseases. This guidance was carried out in the classroom, in a group, with approximately 20 adolescents, providing an environment of discussions on the subjects addressed. The duration was approximately 15 minutes. The elaboration of the video had the participation of three actors, two acting as adolescents and the third as a dental surgeon. The video had a total duration of 14 minutes and was applied in the classroom itself, in a group, with approximately 20 adolescents, without, however, allowing a later discussion of the subject.

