Those responsible for adolescents also answered a questionnaire containing socioeconomic and demographic information according to criteria of the Brazilian Association of Research Companies²⁰.

Oral clinical examination

Clinical examination was performed by a single examiner calibrated ($K \geq 0.83$) and blinded as to the intervention used and which verified the presence of dental biofilm through the simplified oral hygiene index (OHI-S)²¹ and gingival bleeding (GBI)²². The tests were performed in two stages: Phase I and 20 weeks after in Phase V (Figure 1). The subjects were examined in a classroom where they were seated in chairs, and the evaluations were done individually, using gauze, artificial light and a millimeter probe.

Statistical analysis

Statistical analysis was performed on an individual level. Chi-square test was used to analyze the categorical variables. The numerical variables were submitted to the *Kolmogorov-Smirnov* test to verify the normality of the data, obtaining values of $P < 0.05$. Thus, non-parametric tests were used to verify the association between the means of KS, OHI-S and GBI among the different intervention groups. The OHI-S variable was dichotomized in: $OHI-S > 1$ (high dental biofilm index) and $OHI-S \leq 1$ (low dental biofilm index). *Kruskal Wallis* and *Mann-Whitney* tests were used for independent samples and *Wilcoxon's* test for paired samples. The level of significance adopted for all analyzes was 5%. The analyzes were performed using SPSS software version 20.0 (SPSS Inc., Chicago, IL, USA).

[figure not shown]

Figure 1. Flow chart demonstrating the different phases of the study.

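### With 35% loss allowed for, the planned between-arm rank tests do not adjust for baseline KS and no rule covers missing scores, so precision is lost and App comparisons are exposed to bias if loss works differently by arm

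*Combined protocol and SAP*

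**What the plan says.** - **Loss.** Study population and sample size: "Estimating a loss of 35% for each group", after which the target rises from 216 to 317. This is the only place where attrition is addressed.
- **Baseline score.** Interventions: "In Phase I/baseline, the participants answered a questionnaire (pre-test) and were evaluated clinically". Classes are randomised in Phase II, so a pre-randomisation KS is planned for each participant.
- **App.** Two of the four groups receive it for 30 days. The App description says it runs on Android and sends two notifications a day.
- **Tests.** Statistical analysis: Kruskal-Wallis and Mann-Whitney "tests were used for independent samples and" Wilcoxon for paired ones, all on individuals.
- **Silence.** The document gives no analysis population, rule for missing KS, imputation, baseline covariate, comparison of lost with retained adolescents, or sensitivity analysis. It does not say whether the between-arm tests use follow-up KS or change in KS.

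**The concern.** KS is the primary outcome, and the plan allows for about a third of scores to be lost. Kruskal-Wallis and Mann-Whitney need one observed value per adolescent and cannot take a covariate. With no substitute for missing scores, an analyst following the text would most likely compare completers without baseline adjustment.

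Two things are at stake:

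- **Precision.** This is lost even if attrition is harmless.
- **Validity of the App comparisons.** If, say, low scorers drop out of the App arms but not the others, the completers no longer resemble each other at baseline. The arms can then differ with no App effect, even when the percentage lost is the same.

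An arm-specific mechanism is plausible because only the App arms need a compatible phone and carry 30 days of messages.

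**Working it through.** **1. The plan's own figures.** The stated unequal-variance formula gives (2.56² + 1.96²)(1.96 + 0.84)²/0.53² ≈ 291 per group two-sided, not 108. For the loss step, 216/0.65 = 332.3 (333) and 216 × 1.35 = 291.6 (292). Neither is 317, which implies 1 − 216/317 = 31.9% loss. These are separate problems. What follows uses only the 35%, and the pattern is the same at 31.9%.

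**2. Precision.** Let r be the correlation between baseline and follow-up KS (assumed 0.4–0.6; the documents give none). For a comparison of means, SE(adjusted)/SE(follow-up only) = √(1 − r²).
- r = 0.4: √0.84 = 0.917, about 8% smaller.
- r = 0.6: √0.64 = 0.80, 20% smaller.

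Against change scores the ratio is √((1 + r)/2), or 0.837 and 0.894, so adjustment still saves 11–16%.

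**3. Bias with equal loss.** With 35% lost on each side, completer bias = 0.35 × the between-arm difference in (retained mean − lost mean). It is zero when that gap is the same in all arms.

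Assumed inputs: no true effect; SD 1.5; 28 classes of 11, pooled as 14 App v 14 no App (154 a side, about 100 retained); no clustering, to isolate loss; loss related to baseline in the App arms only, odds ratio 1.6–2.7 per SD. The pilot SDs are not used, because 2.56 exceeds 2.5, the largest population SD possible on a 0–5 score.

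For a normal baseline and a logistic retention probability p with slope b = ln(OR), the retained baseline mean moves by m = b × E[p(1 − p)]/0.65 SDs:
- OR 1.6: 0.470 × 0.217/0.65 = 0.157
- OR 2.7: 0.993 × 0.190/0.65 = 0.291

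Bias in follow-up KS = r × 1.5 × m. The SE is 1.5√(2/100) = 0.212 pooled, or 1.5√(2/50) = 0.30 for one App arm against one other arm.

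| OR | r | Bias | Bias/SE, pooled | False positives, pooled | False positives, single arms |
|---|---|---|---|---|---|
| 1.6 | 0.4 | 0.09 | 0.44 | 7% | 6% |
| 2.7 | 0.6 | 0.26 | 1.23 | 23% | 14% |

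Simulation with the Mann-Whitney test agrees: bias 0.10–0.28 and 6.7–24% false positives pooled. With 45% v 25% loss it gives 0.12–0.34 and 8–35%. A second simulation, with a 0–5 beta-binomial score and loss related to baseline in the App arm only, gave bias of 0.21–0.28. False positives were 20–25% with 109 analysed a side and 11–16% with 54.

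**4. When there is no harm.** With loss unrelated to score, error was 4.8–5.4% and bias zero. With the same score-related mechanism in both arms, error was about 4.5–6.8% and bias about zero.

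**5. What adjustment does and does not do.** When loss depends on baseline, regression on baseline brought bias to within 0.02 and error to about 4–6%. When App-arm loss depends on the unseen follow-up score, the second simulation left adjusted bias of 0.20–0.49 and error of 14–75%.

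**6. A common shift is uninformative.** With 35% lost on each side, lowering all lost adolescents by 0.5 or 1 point moves both means by 0.35 × 0.5 = 0.175 or 0.35 × 1 = 0.35. The contrast does not change. Applied to one side only, the same shifts move it by 0.175 or 0.35.

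**The case against.** Several points on the other side stand.

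- **Dropping is not forced.** Rank tests run equally well on imputed or carried-forward scores. The plan never says that adolescents without a score are dropped; that is inferred from its silence. The defect is an omission.
- **The direction is not fixed.** A reader might infer that the App arms would look more knowledgeable. If change scores are tested, bias is −(1 − r) × 1.5 × m, from −0.4 × 1.5 × 0.157 = −0.09 to −0.6 × 1.5 × 0.291 = −0.26, the opposite sign under the same loss.
- **Differential loss is only plausible.** Stopping the App is not the same as missing the follow-up questionnaire. Guidance and examinations took place in classrooms, so ordinary absence could affect all arms alike. With half the log-odds slope in the non-App arms, simulated bias falls to 0.04–0.10 and error to 6–8%.
- **The 0.53 points are not an App benchmark.** They are the pilot difference between oral guidance and video, so the bias should not be expressed as a share of them.
- **The 35% is a planning allowance.** It does not establish that a third of those randomised were lost.
- **The adjusted result is partly built in.** Loss was made to depend on baseline only, and the model tested was a completer regression without clustering, not the mixed model proposed below.

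None of this supplies the missing rule or brings the baseline score into the comparison as a covariate.

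**Conclusion.** The concern holds as a gap in the analysis plan with a conditional risk of bias. The precision loss needs only a pre-post correlation: adjustment cuts the SE by about 8–20% at r = 0.4–0.6. The bias needs loss to relate to score differently in the App arms. Under the assumed inputs it is then about 0.1–0.3 points, with roughly 7–24% false positives for pooled App versus no App, and less inflation for single-arm comparisons (about 6–16%). With unrelated loss, or the same mechanism everywhere and no true effect, there is essentially no bias.

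A reader might conclude that the trial's App result is biased, or that the rank tests make a completer analysis unavoidable. The documents support neither: they report no loss by arm and are silent on missing scores. The sizes rest on an assumed SD, correlation, retention slopes and class size, and clustering is set aside. The point merits a change, at medium confidence; it does not by itself invalidate the trial.

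**What to change.** 1. **Primary between-arm KS analysis.** Use a baseline-adjusted model that allows for class, by allocated arm. One suitable form is a mixed model with baseline and follow-up KS as responses, equal baseline means across arms, and random class and adolescent effects. Keep every randomised adolescent with a baseline score, whether or not the App was installed. The equal-means constraint is reasonable because Phase I precedes allocation.
2. **Reporting.** Give loss by arm, and the baseline KS of lost and retained adolescents by arm.
3. **Sensitivity analysis.** Use multiple imputation with arm-specific shifts: for example, lost adolescents 0.5 and 1 point lower in the App arms only, then in the non-App arms only. This is needed because a common shift cancels under equal loss, and baseline adjustment does not remove bias from loss that depends on the unseen follow-up score.
4. **Rank tests.** If they are kept as secondary, state whether they use follow-up or change scores and how missing scores are treated.

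The cost is SAP wording and modest programming, with no new data collection. The drawback is that the primary model relies on scores being missing at random given baseline; step 3 shows how far the conclusion depends on that.

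### Classes were randomised, but every test treats adolescents as independent, so p-values are too small and the 5% error rate is not held

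*Combined protocol and SAP*

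**What the plan says.** The section on study population and sample size makes the class the unit of allocation: "The randomized allocation was performed using the classes as sample units". It adds: "A total of 28 classes were selected and randomly allocated to an interventional group by a blinded investigator". The Interventions section gives the split as 14 classes to oral guidance and 14 to video, then 7 classes in each of four arms, two of which receive the app. Of the oral guidance it says: "This guidance was carried out in the classroom, in a group, with approximately 20 adolescents". The video was shown in classroom groups of the same size.

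The unit of analysis is stated twice. The study population section says "The analysis was done in the individual unit", and the Statistical analysis section says "Statistical analysis was performed on an individual level". The tests are chi-square for categorical variables, Kruskal-Wallis and Mann-Whitney for independent samples, and Wilcoxon for paired samples, all at 5%. Neither the analysis nor the sample size mentions an ICC, a design effect, a mixed model, GEE, a cluster-robust variance or a class-level summary.

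**The concern.** Kruskal-Wallis, Mann-Whitney and chi-square take each adolescent as an independent observation. Classmates here share a technical course and a classroom session, with discussion in the oral guidance groups, so their outcomes are likely to be correlated. Because whole classes go to one arm, any class effect falls entirely between arms. With 7 classes per arm such effects do not average out well, and these tests read what remains as treatment signal.

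The primary comparison of the knowledge score (KS) is affected, as are the comparisons of the oral hygiene index (OHI-S) and gingival bleeding (GBI). The trial could declare one educational method better because of which classes happened to receive it.

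**Working it through.** **Inputs from the document.** 28 classes; 14 vs 14, then 7 per arm; sessions of about 20; planned total 317; expected loss 35%; significance level 5% (taken as two-sided); KS scored 0 to 5.

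**Assumed.** The ICC is not given, so 0.01 to 0.10 is shown.

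**Class size m.** 317/28 = 11.3 as planned. After losses, 317 × 0.65/28 = 7.4. The session size of 20 is shown as an upper case.

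**The plan's own figures.** The sample size allows nothing for clustering, and it does not reproduce. The stated inputs give (1.960 + 0.842)² × (2.56² + 1.96²)/0.53² = 290.5, so 291 per group and not 108. That is a separate error. Nothing below uses 108; 317 is used only to set m.

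**Formulas.**
- Design effect: DE = 1 + (m − 1) × ICC.
- True error of a nominal 5% two-group test: 2 × [1 − Φ(1.96/√DE)].
- True error of the four-arm Kruskal-Wallis test: P(χ² on 3 df > 7.815/DE).

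Example with m = 11.32 and ICC = 0.05: DE = 1 + 10.32 × 0.05 = 1.516; 1.96/√1.516 = 1.59; true error 11.1%.

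| m | ICC | DE | Two-group error | Four-arm error |
|---|---|---|---|---|
| 7.4 | 0.01 | 1.06 | 5.7% | 6.2% |
| 7.4 | 0.02 | 1.13 | 6.5% | 7.4% |
| 7.4 | 0.05 | 1.32 | 8.8% | 11.5% |
| 7.4 | 0.10 | 1.64 | 12.5% | 18.9% |
| 11.3 | 0.01 | 1.10 | 6.2% | 6.9% |
| 11.3 | 0.02 | 1.21 | 7.4% | 9.1% |
| 11.3 | 0.05 | 1.52 | 11.1% | 16.1% |
| 11.3 | 0.10 | 2.03 | 16.9% | 27.9% |
| 20 | 0.02 | 1.38 | 9.5% | 12.9% |
| 20 | 0.10 | 2.90 | 25.0% | 44.1% |

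**Simulation of the planned tests.** A normal variable with the given ICC was cut to a 0 to 5 score, with 28 classes of 11, no true effect and 1,500 runs per row. Simulation error near 5% is about ±1.96 × √(0.05 × 0.95/1500) = ±1.1 points.

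| ICC | Mann-Whitney, 14 vs 14 | Mann-Whitney, 7 vs 7 | Kruskal-Wallis, 4 × 7 | Class-mean t-test, 14 vs 14 | Class-mean ANOVA, 4 × 7 |
|---|---|---|---|---|---|
| 0 | 4.6% | 4.4% | 3.8% | 5.1% | 4.6% |
| 0.01 | 6.4% | 6.5% | 6.3% | 5.4% | 4.8% |
| 0.02 | 7.1% | 7.5% | 7.0% | 5.5% | 4.3% |
| 0.05 | 10.6% | 8.3% | 14.0% | 5.5% | 5.5% |
| 0.10 | 15.5% | 14.0% | 22.7% | 4.8% | 4.3% |

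Repeat simulations at 11 per class put Kruskal-Wallis at about 7% to 9%, 13.5% to 16% and 23% to 27% for ICC 0.02, 0.05 and 0.10. With 7 per class it was about 7%, 11% and 17%. At ICC 0 the planned tests sit near or slightly below 5%, so the inflation comes from the clustering.

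**The case against.** - **The ICC is unknown and the low end is mild.** This stands as a limit on size. At ICC 0.01 the simulated error is about 6% with 11 per class, and 5.5% for Kruskal-Wallis with 7 per class. But any positive ICC inflates the error, and the plan gives no evidence that the ICC is negligible.
- **Individual-level analysis is legitimate in a cluster trial.** It is, if the method carries class. None of the listed tests does.
- **Group teaching is only part of the picture.** App messages went to individual phones, one session per class is an inference, and the Interventions section opens by describing delivery to individuals inside each class. That last statement conflicts with the classroom description and should be reconciled. Randomisation by class calls for a cluster-aware analysis on its own.
- **m = 20 does not fit the sample.** 28 × 20 = 560, against 317 planned. Those rows are an upper case, and the conclusion rests on 7.4 and 11.3.
- **Mann-Whitney inflates less than Kruskal-Wallis.** This is true at the higher ICCs, and both are shown.
- **Wilcoxon is not quantified.** This is fair. A class effect that is stable over time cancels in within-person change, so only class-level variation in change matters. The test still treats classmates' changes as independent.
- **The document cites the cluster extension of CONSORT.** It does so for how the trial is described, so that is no evidence of a breach. It does show that the trial is presented as cluster randomised.

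**Conclusion.** The concern holds, and the analysis is wrong as written. The stated 5% level is not held by the between-arm tests whenever the ICC is positive. For assumed ICCs of 0.02 to 0.10 and the planned 11.3 per class, the true error is 7.4% to 16.9% for a two-group comparison, with a larger excess for Kruskal-Wallis at the upper end of that range. After 35% loss the two-group range is 6.5% to 12.5%. The exact size depends on ICCs that only the trial data can supply. The direction does not, and the defect reaches the primary outcome.

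**What to change.** State in the Statistical analysis section that all between-arm comparisons account for randomisation by class, and name the method:

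- **KS, OHI-S and GBI.** The option closest to the plan is a rank or permutation test on the 28 class means, permuting classes in line with the two-stage allocation. Comparing 7 with 7 classes allows C(14,7) = 3,432 arrangements, enough for a test at 5%. The alternative is a linear mixed model with a random intercept for class and small-sample degrees of freedom, which also allows adjustment for baseline KS.
- **OHI-S above 1.** Use logistic GEE clustered on class, with a small-sample correction. With 7 classes per arm the correction is essential.
- **Change within an arm.** Replace the individual Wilcoxon test with one on class-mean changes. With 7 classes the smallest two-sided p-value is 2/2⁷ = 0.016, so 5% is attainable.
- **Reporting.** Give the ICC for each outcome and the number of classes and adolescents analysed per arm.

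The study ran from July to December 2016 and the document is dated July 2018, so this is a re-analysis and should be labelled as one. The cost is revised wording and a re-run. It needs no new data, provided that class was kept for each participant, which allocation by class makes likely but the document does not state. P-values will generally rise. At 11.3 per class, 317 adolescents carry the information of about 317/1.206 = 263 (ICC 0.02) to 317/2.032 = 156 (ICC 0.10) independent ones.

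### Baseline KS, OHI-S and GBI are collected but not used in the named between-arm tests: a possible loss of precision, not bias

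*Combined protocol and SAP*

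**What the plan says.** The Interventions section has pupils complete the questionnaire and a clinical evaluation at Phase I, and both again after the app period. The Questionnaires section makes KS, scored 0 to 5, the primary outcome. The Oral clinical examination section also describes two examinations: "The tests were performed in two stages: Phase I and 20 weeks after in Phase V".

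The Statistical analysis section opens with "Statistical analysis was performed on an individual level". It uses chi-square for categorical variables. After a normality check it continues: "Thus, non-parametric tests were used to verify the association between the means of KS, OHI-S and GBI among the different intervention groups". Kruskal-Wallis and Mann-Whitney are named for independent samples, and Wilcoxon's "test for paired samples". On the hygiene index it adds "The OHI-S variable was dichotomized in" values above 1 and values of 1 or less.

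No covariate or adjusted model is named. The section does not say whether the independent-sample tests use follow-up values or changes, and it names no between-arm difference with a confidence interval. The Study population and sample size section does plan in points: "the difference detected between the groups was 0.53 points in the knowledge score".

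**The concern.** The only named test that links the two time points is the paired Wilcoxon, which gives a before-after comparison. It is not a baseline-adjusted contrast between arms. Baseline values of all three outcomes are in hand, yet nothing in the named between-arm comparison uses them.

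What is at stake is mainly precision. With 28 classes allocated (14 oral versus 14 video, then 7 per arm), baseline differences between arms arise by chance, and adjustment removes the part of the error that baseline predicts.

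Two smaller gaps come with this:

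- A rank test on follow-up values and one on changes are different analyses, so the primary comparison can be read in two ways.
- Without an estimate in KS points and an interval, a reader cannot tell whether the oral versus video result is compatible with 0.53 points. This is a reporting gap and costs no precision in itself.

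**Working it through.** **The plan's own figure.** The Study population and sample size section gives no figure for baseline adjustment. Its sample size does not reproduce: (2.56² + 1.96²) × (1.960 + 0.842)² / 0.53² = 290.5, so 291 per group two-sided, against the stated 108. The loss step does not reproduce either: 216/0.65 = 332.3, so 333, against "Estimating a loss of 35% for each group, the final sample totaled 317 individuals". That is a separate matter. It enters here only through class size, so a range is shown.

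**Inputs from the documents.** There are 28 classes in four arms of 7. Pupils per class, m, is 317/28 = 11.3 as the base case. The alternatives are 216/28 = 7.7 (the stated number before the loss allowance) and 20 (the approximate size of the classroom sessions). Spreading 317 over all 28 classes is itself an assumption, because 317 comes from a two-group calculation.

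**Assumed inputs (not in the documents).** Within-class baseline to follow-up correlation r = 0.5, ICC = 0.05, and class-level correlation rc = 0, 0.5 or 0.9. Baseline and follow-up are given equal SD and ICC.

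**Formulae.** Whole classes are allocated, so the correlation that matters is that between class means:

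R = [rc × ICC + r × (1 − ICC)/m] / [ICC + (1 − ICC)/m]

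Variance ratio, adjusted to unadjusted = (1 − R²) × (1 + 1/22)

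The second factor is the cost of estimating the slope from 28 classes in four arms (24 degrees of freedom).

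**Base case, m = 11.3.** (1 − 0.05)/11.3 = 0.0841, so the denominator is 0.1341.

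- rc 0: R = 0.0420/0.1341 = 0.313; ratio = 0.902 × 1.0455 = 0.943.
- rc 0.5: R = 0.500; ratio = 0.750 × 1.0455 = 0.784.
- rc 0.9: R = (0.0450 + 0.0420)/0.1341 = 0.649; ratio = 0.579 × 1.0455 = 0.605.

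Confidence interval width is √ratio × 2.069/2.064 (t on 23 versus 24 degrees of freedom): 0.973, 0.888 and 0.779. The interval is therefore about 3%, 11% or 22% narrower.

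**Variance ratio by class size (r 0.5, ICC 0.05)**

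| m | rc 0 | rc 0.5 | rc 0.9 |
|---|---|---|---|
| 7.7 | 0.913 | 0.784 | 0.649 |
| 11.3 | 0.943 | 0.784 | 0.605 |
| 20 | 0.983 | 0.784 | 0.526 |

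**Unfavourable end.** Over r 0.3 to 0.6 and ICC 0.01 to 0.10, the worst case is r 0.3, ICC 0.10, rc 0, m 20. There R = 0.0135/0.145 = 0.093 and the ratio is 0.991 × 1.0455 = 1.036, a variance increase of about 4%.

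**Chance imbalance.** With equal SDs and ICCs, the class-mean slope is R. A baseline difference of one standard error (SE) then carries over R × SE, with variance R² × SE². That is the same R² that adjustment removes above.

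**Follow-up or change.** The variance of a change relative to a follow-up value is 2(1 − R). At m 11.3 this is 1.37, 1.00 and 0.70 for rc 0, 0.5 and 0.9, so neither reading is uniformly better. Null trials were simulated with a 0 to 5 score, 28 classes of 11 and r 0.5, using pupil-level Mann-Whitney tests of 14 versus 14 classes. The two readings gave different 5% verdicts in about 8% of runs at ICC 0, where both tests hold about 5%. At ICC 0.05 they differed in about 15%, but there each test also rejects in roughly 9% to 14% of null runs.

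**The case against.** The strongest reply is that an unadjusted comparison under randomisation is valid, so adjustment is a preference. Every driver of the gain is assumed, and in one plausible case the interval narrows by only 3%. That stands as a limit on the size of the point. It does not remove it, because the baselines are already collected and using them needs no new data.

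Four stronger readings are tempting and are not supported:

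- **Bias.** Nothing in the documents shows that leaving out baseline biases the arm comparison.
- **A gain of 1 − r².** With r 0.5, a reader might expect a 25% cut in variance, as in a trial that randomises individuals. Here classes are allocated, and the class-level correlation is unknown.
- **Imbalance as a second harm.** It is the same baseline-explained variance and should not be counted again.
- **The 15% disagreement as the cost of an undefined test.** Nearly half of it comes from analysing pupils individually when classes were allocated, which is a separate and larger problem. About 8% belongs to the ambiguity alone.

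Nor do the documents say that the methods will be compared through within-arm Wilcoxon tests. They leave the use of that test open.

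**Conclusion.** The point holds as a possible loss of precision. At r 0.5, ICC 0.05 and 11.3 pupils per class, adjustment would cut the variance of the 14 versus 14 contrast by about 6% to 40%, depending on a class-level correlation that the documents do not give. Under the wider assumptions it could instead raise the variance by up to about 4%. The direction is therefore likely but not assured.

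The unstated choice between follow-up values and changes is secondary and real. The missing difference with a confidence interval is a reporting gap. Baseline adjustment does not repair the individual-level analysis: with a design effect of 1 + (11.3 − 1) × 0.05 = 1.52, the adjusted variance is still 1.52 × 0.943 = 1.43 times (rc 0) or 1.52 × 0.784 = 1.19 times (rc 0.5) what unadjusted individual-level tests assume.

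The follow-up value itself also needs defining. The Interventions section describes four phases, with clinical reassessment in phase IV shortly after the 30 days. The Oral clinical examination section puts it at 20 weeks in Phase V. Figure 1 is not available to settle this.

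**What to change.** Beside the original tests, and labelled post hoc:

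1. Analyse follow-up KS by arm adjusted for baseline KS (class mean plus the pupil's deviation from it), with class as a random effect and a small-sample correction for 28 classes. The equivalent class-level analysis would also serve.
2. Report adjusted differences in KS points with 95% confidence intervals.
3. Do the same for OHI-S and GBI, each with its own baseline.
4. State whether each retained rank test used follow-up values or changes, and do not compare methods by within-arm Wilcoxon tests.
5. Reconcile the two accounts of follow-up timing before defining the follow-up value.

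An ordinal mixed model, or a permutation test that re-allocates whole classes, is an optional sensitivity analysis.

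The cost is analysis and reporting time. "The duration of the study was from July to December 2016" and the document is dated 2018, so this cannot be presented as prespecified. There may be no precision gain, or a variance increase of up to about 4%, if baseline does not predict follow-up at class level.
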